We acknowledge that our sample sizes will be small given the low incidence of PKAN in the general population. Thus, our focus will be on estimating the magnitude of effects to capture disease progression and reaction to intervention. We will explore correction techniques for small sample size, such as bootstrapping, shown to work with similar models with small sample sizes (e.g., $N = 33$), as well as Bayesian analyses. We will handle missing data with full information maximum likelihood estimation, which will lessen the risk of bias and loss of power due to missing data.

Data analysis

Our clinical experience with PKAN has informed our approach. We expect to observe differences from one subject to another in their initial functional status and in the rate of change in functional status after intervention. Furthermore, we know that children with PKAN will first gain and then lose function over time. The use of LGC models allows for both variable-centered and subject-centered elements in the analysis. This is critical given our prediction that subjects will demonstrate different patterns of disease progression and may have individual differences in responding to treatment. Our modeling strategy does not rely on an assumption of uniformity in progression rate or treatment effects and allows for flexible multivariate growth curve models to be constructed, allowing us to capture subtleties in disease progression and influences (e.g., a disease-modifying intervention) on it that might be masked by traditional analyses. This approach will allow us to examine change at the group level while modeling individual differences in initial functional status and change in function over time. We will be able to examine trajectories of motor, cognitive, social, language and adaptive functioning to track developmental milestone attainment and loss and determine if these are linear or non-linear. We will be able to determine whether a putative disease-modifying agent alters the natural history of the disease. In addition, we will assess the sensitivity of individual measures (e.g., upper extremity function score) compared to a combination of measures (e.g., global mobility score) to detect change. This will inform refinement of models and measures to

capture accurately fast vs slow disease progression monitoring and responses to intervention levels.

Constructing the model

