We will use the Mplus software (v.8) to estimate LGCs including robust standard errors and corrected chi-square values to handle non-normality and missing data as needed. The model parameters of interest will be the overall level of skill or ability (i.e., intercept) and amount of change (i.e., slope) for the domain assessed. The basic model, a starting point, is defined as:

$$Y_{it} = \alpha_{yi} + \beta_{yi}\lambda_t + \epsilon_{it},$$

where Y_{it} is assumed to represent the repeated measures (motor domain), where i stands for a person, t represents the time-ordered measurements, α_{yi} is defined as the initial functioning status on a given domain for a person's trajectory and β_{yi} is the slope representing change. In addition, λ_t represents the measured time points and ϵ_{it} represents the residual for each person. This base model allows one to develop more complex models of linear or non-linear trajectories, including covariates (e.g., age, mutation, intervention). Several indices will be used to evaluate model fit, including indices such as: chi-square (χ^2), Comparative Fit Index (CFI), and the Standardized Root Mean Squared Residual (SRMR). For example, a CFI value greater than or equal to 0.95 with a SRMR value at or below 0.05 indicate excellent fit.

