Three broad steps will define model building and trimming. First, trajectories of the domains of interest will be examined in unconditional LGCs. We will explore both linear and non-linear models to determine what best captures change and compare these models statistically for best fit. Next, we will combine the single models into a multivariate unconditional model across domains where the parameter estimates are obtained controlling for other variables in the model. For example, the estimates of baseline status of cognitive functioning in the unconditional multivariate model will control for the baseline levels of the motor functioning. This will allow for the correlation between the initial levels of functioning and change in these in functioning to be estimated, enabling us to understand the shape and level of change. Finally, we will add covariates (e.g., intervention group) to models. It is the conditional multivariate LGC where the influence of - or differences due to - these covariates on initial status and rates of disease progress can be estimated. We will also use recent work in this area to enable re-parameterization of such models to make the results more meaningful in terms of the parameter estimates reflecting quantities of interest to daily functioning. This modeling process will allow us to trace the disease progression over various patient functioning variables, the influence of the intervention on the change trajectory, and begin to understand how disease progression of PKAN occurs at the aggregate and individual level. The product of this effort will be a robust model and parameter estimates of the natural history of PKAN with key outcomes that can inform the variability in the intervention effects while controlling for other variables. Model estimates will be essential for the planning of larger scale studies of compounds with putative disease-modification effects such as 4'-PPT.

d. Other analyses

Adherence and retention analyses

Adherence will be defined as the proportion of product consumed in each study time period, averaged over all periods with weighting to compensate for uneven spacing of collection points.

eIRB 18782 CoA-Z in PKAN (NIH)

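### The unconditional joint growth-curve model is said to adjust cognitive estimates for motor function, but as specified it gives marginal trajectories with correlated domains

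*Combined protocol and SAP*

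**What the plan says.** Section 10.c of the combined protocol and SAP, under Constructing the model, starts from a single-domain curve whose parameters of interest are "the overall level of skill or ability (i.e., intercept) and amount of change (i.e., slope) for the domain assessed". Model building then has three steps: unconditional curves for each domain, a joint model, and a conditional model with covariates.

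The second step is to "combine the single models into a multivariate unconditional model across domains". The plan makes the adjustment claim about this step twice. In general terms, it says that "the parameter estimates are obtained controlling for other variables in the model". As an example, it says that "the estimates of baseline status of cognitive functioning in the unconditional multivariate model will control for the baseline levels of the motor functioning".

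The next sentence describes the output differently: "This will allow for the correlation between the initial levels of functioning and change in these in functioning to be estimated". Covariates, with intervention group as the example, enter only in the third step. Nowhere does the section specify a path from a motor factor to a cognitive factor.

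**The concern.** Allowing two domains to correlate and adjusting one for the other are different operations that answer different questions. A marginal cognitive trajectory describes how cognition starts and changes in the group as a whole. A motor-adjusted one describes cognition among people with the same motor status, or cognitive change beyond what accompanies motor change. In a disease where motor disability is prominent, a reader told that cognitive estimates control for motor function could take them as cognitive involvement separate from motor involvement. The specified model does not support that interpretation. The plan intends the growth-curve work to inform later studies, so the label on each estimate matters even though the aim is exploratory.

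**Working it through.** The documents give no numerical growth-curve result to reproduce, so the check is structural, followed by an illustration.

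**Inputs from section 10.c.** The basic equation is Y_it = α_i + β_i λ_t + ε_it. The time scores λ_t carry no person index, so they are common to all participants. The joint step has no covariates and links domains by correlation.

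**Step 1: what the joint model contains.** Take motor (m) and cognitive (c). Each participant has four growth factors (α_m, β_m, α_c, β_c) with mean vector μ and covariance matrix Ψ. Motor function reaches the cognitive part only through the off-diagonal elements of Ψ. The cognitive baseline parameters are E(α_c) and Var(α_c), with nothing held fixed.

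**Step 2: what adjustment would require.** A regression is needed: α_c = a + b α_m + ζ, with b = Cov(α_c, α_m) / Var(α_m) and Var(ζ) = Var(α_c) − b² Var(α_m). The quantities a, b and Var(ζ) are not the reported intercept mean and variance.

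**Step 3: why joint and separate estimates coincide.** The same matrix Λ (a column of ones and the time scores) carries both the means and the random factors. Stack the domains with Z = I ⊗ Λ, so that V = ZΨZ′ + R. The generalised least squares estimate of μ then reduces to (Z′R⁻¹Z)⁻¹Z′R⁻¹ȳ, in which Ψ does not appear. If residuals are independent across domains with constant variance within a domain, this splits by domain. With complete data, each domain's means are therefore those of its own separate fit.

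**Step 4: numerical illustration.** One data set was simulated with 64 participants, four occasions, two domains, complete data and assumed parameter values. Maximum likelihood was used for the separate and joint linear models.

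| Cognitive quantity | Separate fit | Joint fit |
|---|---|---|
| Intercept mean | 40.82 | 40.82 |
| Slope mean | −3.74 | −3.74 |
| Intercept variance | 84.34 | 84.34 |

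Conditioning on the motor intercept (joint-fit mean 49.20) gives b = 0.758 and Var(ζ) = 34.70, which is 34.70 / 84.34 = 41% of the marginal variance. The regression constant is a = 3.51. At the average motor level the adjusted mean returns to the marginal mean: 3.51 + 0.758 × 49.20 = 40.80, which is 40.82 apart from rounding of b. In this illustration, adjustment therefore changes the spread and the meaning of the parameters, not the mean at average motor level.

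**Step 5: missing data.** Section 10.c plans full information maximum likelihood. With incomplete records the joint fit can use motor scores to inform missing cognitive scores, so joint and separate estimates may differ numerically. The parameters are still E(α_c), E(β_c) and their variances, so the target remains marginal.

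**The case against.** The strongest defence is that this is a loose gloss on a model otherwise described correctly. The next sentence gives correlations as the output, and covariate influence is reserved for the conditional step. An unrestricted Ψ also contains what is needed to derive b and Var(ζ) afterwards. Finally, the aim concerns feasibility, and the remark that model estimates will be essential for larger studies follows the product of all three steps, not this one alone.

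Much of this stands and limits the consequence. It does not rescue the claim, which is made twice and attached to the baseline estimates themselves. Those estimates are not adjusted, and the plan describes no derivation that would make them so.

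A reader might also infer that the joint model is too large to fit. Section 10.c (Data analysis) speaks of "trajectories of motor, cognitive, social, language and adaptive functioning". Five domains with linear slopes and unrestricted covariances would need at least 10 means + 55 variances and covariances + 5 residual variances = 70 parameters, against 64 enrolled or 60 completing in the Primary Cohort. The documents do not support treating this as an error:

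- They never say that all five domains enter one model. The only worked example has two, which needs 4 + 10 + 2 = 16 parameters.
- They fix no covariance structure and provide for trimming. Four linear domains need 8 + 36 + 4 = 48. Five domains with only intercept–intercept and slope–slope links across domains need 10 + 15 + 20 + 5 = 50.
- The data are natural history data from a separate protocol, with no sample size given. Trial participants alone could number up to 64 + 86 = 150.
- A count above the number of participants does not by itself leave the model unidentified. With four occasions (assumed), five domains supply 20 × 23 / 2 = 230 observed moments.

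Convergence failure was not tested. It remains a risk to watch.

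**Conclusion.** The point holds for the adjustment claim. Both statements attribute to the unconditional joint model a property that it lacks. That conclusion rests only on the specification in section 10.c: correlated growth factors, with no directed path between domains. It does not depend on the simulated values. Exact agreement between joint and separate estimates needs more, namely complete data, common time scores and the simple residual structure used above.

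The effect is on what the exploratory results may be said to show. Its size in PKAN cannot be given, because it depends on the unknown motor–cognitive correlation; the 41% is illustrative. It should not be stretched to a claim that the growth-curve aim is infeasible, since the number of domains, the covariance structure and the sample are all left open. The safety, tolerability and CoASY analyses do not use this model.

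**What to change.** Replace both adjustment statements with one saying that the unconditional joint model gives marginal trajectories for each domain and the between-domain correlations of level and change.

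If motor-adjusted cognitive status or change is of interest, add to the conditional step a regression of the cognitive intercept and slope on the motor intercept and slope, and label only those results as adjusted. If intervention group is in the same model, its coefficient on cognitive slope will exclude any effect running through motor change, so it should be shown beside the version without the motor factors.

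The cost is a text change and, if adjustment is wanted, one extra exploratory model. No data collection, sample size or confirmatory analysis changes. Stating which domains enter the joint model, and the growth-curve data set, would also let readers judge its size; this is a suggestion and not a condition.
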